5.4. Intervention

5.4.1. Intervention delivery in Arms 1 and 2

[figure not shown]
The in-person counseling using the EXTEND study workbook, the live phone call boosters, and training in the use of the tech boosters will be delivered by a counselor trained in HIV/AIDS counseling (Uganda Ministry of Health) after the baseline survey and blood draw. The EXTEND study workbook, which was adapted to the Ugandan local context from the TrEAT/HWHL intervention by the EXTEND study team, will serve as a scripted guide for the in-person counseling session. The counselor will be trained by [name] in techniques to conduct the alcohol counseling

sessions; training will include mock counseling sessions. While this is not an MI intervention, [name] experience and training in Motivational Interviewing will be useful in the motivation component of the intervention. The in-person sessions will be audio-recorded and 15% will be reviewed by the Ugandan project coordinator for fidelity, using a check-list of intervention components as in previous alcohol intervention trials.^{23,125}

Participation of support person/helper: Part of the study intervention involves asking study participants whether they can identify a support person or helper, to help support them with their drinking goals. Participants in the intervention arms (Arms 1 and 2) will be asked to identify a support person or helper who is a friend or relative who can support them with their drinking goals. If there is someone they can call on to be a helper, we will ask them to bring them in to participate in their second in-person counseling session. The person identified will be given some information by the counselor to guide them in supporting the participant.

For those in the live phone call booster arm, the counselor will schedule the first live booster call and make a test call to the participant's phone. During the intervention period, the counselor will try to reach the participant 3 times for each booster session, at different times of day or evening, and will try to reach up to 3 of the participants' contacts as needed. The counselor will use the script for the call (see appendix), complete a check-list of the script components, and record all attempted and completed calls in a database designed for this purpose.

For those in the technology booster arm, the counselor will obtain information for the tailoring variables during the in-person session, and will enter them into the technology program interface. The counselor will engage in demonstrations of the SMS and IVR boosters and a discussion of the pros and cons of each, to help participants decide which they prefer, based on their level of literacy, need for confidentiality, and other considerations. After the choice is made, the counselor will provide further training on using SMS or IVR, entering a PIN# to obtain the messages, and responding to the questions. As was effective in increasing engagement in previous tech interventions,¹²⁶ the counselor will send a test SMS or IVR message to Arm 2 participants and watch them enter the PIN# and access and respond to the message, assisting and sending another message as needed. The counselor will also show those choosing SMS how to delete the SMS from their phones after the session. The data manager will monitor SMS/IVR session completion; if there is a 3-week interval with no tech booster session interaction, the data manager will alert the counselor who will call the participant and his/her contacts to verify if the cell phone number is still correct. Participants in both booster arms will receive reminders before they are due for their 2nd in-person counseling session, which will be scheduled to coincide with their next clinic visit.

5.4.2. Intervention delivery in Arm 3

Participants randomized to Arm 3 (SOC) will have no contact with the study counselor for the duration of the trial (9 months). However, at their 9-month study visit, and at the end of their study participation as randomized, they will be offered the intervention and given a choice of the delivery method for the booster sessions. Although the study counselor will deliver the intervention at this time point, we will not collect intervention data associated with this group.

Table 2. RCT study visit and intervention schedule

Study enrollment, baseline questionnaire, DBS collection, and randomization			
Month 0	Arm 1: In-person counseling plus live booster (n=90)	Arm 2: In-person counseling plus tech booster (n=90)	Arm 3: SOC control (n=90)
	In-person counseling session	In-person counseling + tech training	Standard care
Months 1-3	Live booster (every 3 weeks over 12 weeks)	Tech booster (1X to 2x/week over 12 weeks)	---
	In-person counseling session	In-person counseling session	Standard care
Month 3	One third of a subset (n=8-12 per arm): qualitative semi-structured post-intervention interview		
Month 5	Phone call reminder to attend 6-month study visit		
Month 6	Follow-up survey, DBS collection		
	Two thirds of a subset (n=8-12 per arm): qualitative semi-structured post-intervention interview		
Month 8	Phone call reminder to attend 9-month study visit		
Month 9	Follow-up survey, DBS collection		
	Follow-up survey, DBS collection	Follow-up survey, DBS collection	Alcohol intervention offered

5.5. Study visits

Baseline survey and randomization: All participants will undergo collection of contact information, a 30-minute baseline survey, and collection of blood spots for PEth and HIV viral load testing. After these activities, randomization will be conducted by the study coordinator (to keep the RAs blinded) using previously prepared sealed envelopes, in blocks of 9 to spread out the burden of the live boosters. Those randomized to Arms 1 or 2 will be referred to the study counselor for in-person counseling and training on the booster modes. Those randomized to Arm 3 will have no contact with the study counselor.

Six-month follow-up visit. Six months after baseline, we will conduct DBS collection and a quantitative survey, measuring alcohol consumption, and domain characteristics (Table 3).

Nine-month follow-up visit. Nine months after baseline, we will conduct DBS collection and a quantitative survey, measuring alcohol consumption, intervention usability and satisfaction, social desirability, and domain characteristics (Table 3). After data and specimen collection, those in the control arm will be offered the intervention, and will be allowed to choose their preferred method of booster delivery. We will also conduct **IDIs** with 8-12 participants per study arm. These participants will be selected using the a priori categories, with roughly equal numbers of those receiving boosters by SMS and by IVR within Arm 2. The aim of the IDIs will be to explore acceptability and experiences with all three study arms, including the two modes of tech delivery. These interviews will be coded and analyzed using the methods described below (statistical analysis plan).

Individual in-depth interviews at 3-6 months: Following participation in the intervention phase of the trial, a select number of participants (8-12 per study arm) will be invited to participate in a follow-up one-on-one, semi-structured qualitative interview with a research assistant. One third of these participants will participate in the qualitative interview

within 0-1 month post intervention, i.e., between month-3 and month-4 from their baseline study visit. The remaining two thirds of the participants selected to participate in the post-intervention qualitative interviews will participate at 3 months post intervention, i.e., at month-6, which is 6 months from their baseline study visit. The 1/3 group will offer more insights on intervention experiences as recall will be fresher, and the latter 2/3 group will be able to help us understand longer term impacts and the multiple factors that influence outcomes (including but not limited to intervention).

The research assistant will ask them about their experience with and perceptions of the trial as well as the different components of the intervention. The interview will last about 60 minutes and will take place either at a private location. We will audio-tape the individual interview and the recordings will be transcribed. The recordings will be transferred to a computer where they will be secured by a password, and the recordings will be destroyed following transcription.

Retention: We have had 90% six-month retention in our previous studies in this setting.⁷ As in the past, we will collect contact information such as cell phone numbers of participants and their friends and family that will be stored in a database that generates automated tracking reports and lists. We will obtain permission to access the participants' medical records to determine the date of their next clinic appointments, and their charts will be flagged so that the RAs will be notified when they come to the clinic so they may receive the study visit. We will provide air time to clinic staff so they can call us if a participant returns to clinic. Follow-up tracking will be conducted by phone calls and home visits (if other methods fail) to participants and their contacts. The RA will call participants at month five to remind them to attend the 6-month study appointment.

Table 3. Quantitative survey variables

Domain	Base-line	6 Months	9 Months	Individual variables
Demographics	X			Age, sex, religion, household assets (as a measure of SES), ¹³⁰ occupation
Health	X	X	X	Medical Outcomes Study-HIV scale for quality of life and overall physical and mental health functioning, ¹³¹⁻¹³⁵ body mass index, ART adherence Single Item Rating Scale. ^{136,137} From Clinic: CD4 cell count, ART status, and MUST pharmacy pill count.
Literacy, cell phone use	X			Ability to read this sentence when shown ("Please read this sentence out loud"), hours phone turned on and charged, SMS use, phone sharing
Alcohol use	X	X	X	AUDIT-C, drinking patterns, beverage-specific typical and maximum drinking, ¹³⁸ 3 week timeline follow-back ¹³⁹
Psychosocial variables/scales	X		X	Social support, ¹⁴⁰ HIV stigma, ¹⁴¹ Center for Epidemiologic Studies Depression Scale (16 items), ¹⁴² Stages of Change Treatment Eagerness Scale (19 items), ¹⁴³ Marlowe Crowne Social Desirability Scale (11 items, baseline and follow-up) ¹⁴⁴
Intervention characteristics			X	Client Satisfaction Scale-8 (8 items) ¹⁴⁵ , System Usability Scale (10 items) ^{146,147} Perceived Awareness of the Research Hypothesis Scale (demand characteristics; 4 items) ¹⁴⁸

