4.1. Study setting

The EXTEND study will be conducted at the Immune Suppression Syndrome (ISS) Clinic of the Mbarara Regional Referral Hospital (MRRH) in southwestern Uganda. The adult HIV prevalence in Southwest Uganda is 8% and heavy alcohol use is common while other substance use is rare. There are over 12,000 active patients at the ISS Clinic; 25% are current drinkers. The ISS Clinic and pharmacy use electronic medical records (EMR) that will be leveraged for patient recruitment, and tracking.

5. Study Procedures

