5.2. Screening

Participants will be recruited from the ISS clinic by a clinic staff member. This person will examine clinic records to identify those who are coming in for appointments who meet study criteria. Persons meeting these pre-screening eligibility criteria will be invited to meet with a study RA. Those who agree will be screened to determine further eligibility criteria by the RA. Following the screening, the RA will seek informed consent from individuals who meet the inclusion criteria below for further study participation. The baseline visit will include collection of tracking information, a baseline survey, and blood draw. Participants randomized to the intervention arms of the study will complete session 1 of the intervention.

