Randomization will be 1:1:1 and will be conducted by the study coordinator and the data manager (to keep the RAs blinded) using pre-printed scratch cards revealing the randomization arm, in blocks of 10 to spread out the burden of the live boosters. Those randomized to Arms 1 or 2 will be referred to the study counselor for in-person counseling and training on the booster modes. Those randomized to Arm 3 will have no contact with the study counselor.

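### Two different fixed block sizes are printed, neither varied nor withheld from recruiting staff, so at this single clinic up to about a fifth of allocations could be known in advance as counselor or no counselor

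*Combined protocol and SAP*

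**What the plan says.** All references are to the combined protocol and SAP.

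- **Section 5.5 (baseline survey and randomization):** the study coordinator allocates "using previously prepared sealed envelopes, in blocks of 9 to spread out the burden of the live boosters".
- **Section 5.3:** allocation is 1:1:1, by the study coordinator together with the data manager, "using pre-printed scratch cards revealing the randomization arm, in blocks of 10 to spread out the burden of the live boosters".
- Both sections give keeping the research assistants (RAs) blinded as the reason why other staff allocate. Neither mentions varying the block size or withholding it.
- **Visible consequence of allocation:** "Those randomized to Arms 1 or 2 will be referred to the study counselor for in-person counseling and training on the booster modes", whereas "Those randomized to Arm 3 will have no contact with the study counselor". Section 5.2 places the first session with the baseline visit: "Participants randomized to the intervention arms of the study will complete session 1 of the intervention".
- **Setting and pace:** one clinic (section 4.1), with one or two enrollments a day considered feasible (section 5.3).
- **Who recruits:** a clinic staff member who also belongs to the research team makes the first approach (section 5.1). An RA then completes eligibility and takes consent (sections 5.1 and 5.2). Randomization follows the baseline survey and blood collection (section 5.5).

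**The concern.** A constant block size lets anyone who can follow past assignments count down to the end of each block. At one or two enrollments a day, a block of 9 fills in roughly 5 to 9 enrollment days, which is short enough to track. Referral to the counselor, at about the time of allocation, separates Arms 1 and 2 from Arm 3.

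If a recruiter can foresee what the next person will receive, that knowledge can influence whom to approach, how borderline eligibility is judged and how consent is discussed. The arms may then differ in who entered them, for example in readiness to change. The trial is meant to supply effect sizes for a larger study (section 5.9), so such a difference would carry forward. The only stated reason for blocking is to spread the live-booster workload, and that does not require a constant size.

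**Working it through.** **Inputs.** Block size 9 (section 5.5) or 10 (section 5.3); ratio 1:1:1 (section 5.3); 270 participants, 90 per arm (Table 2 and section 5.9.1); counselor contact for Arms 1 and 2 only (sections 5.3 and 5.5). The documents give no figure for predictability, so there is none to reproduce.

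**Fit to the planned arm sizes.** 270/9 = 30 blocks of 3:3:3, which gives exactly 90 per arm. 270/10 = 27 blocks, but 10/3 is not a whole number, so each block must be uneven (4:3:3 is assumed below). The total reaches 90 per arm only if the extra place rotates evenly.

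**Certain allocations, blocks of 9, all earlier arms known.** An allocation is certain when every remaining place in the block belongs to one arm. For the last j places, P = 3 × C(9−j, 3−j) / C(9,3), with C(9,3) = 84.

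- 9th place (j=1): 3×28/84 = 1
- 8th place (j=2): 3×7/84 = 0.25
- 7th place (j=3): 3×1/84 = 0.036
- Sum 1.286 per block; 1.286/9 = 14.3%; × 30 blocks = about 39 of 270

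**Certain allocations, blocks of 9, only referral seen (6 counselor, 3 none).** P = [C(9−j, 6−j) + C(9−j, 3−j)] / 84.

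- Remaining places all counselor, j=1 to 6: (56+35+20+10+4+1)/84 = 126/84 = 1.50
- Remaining places all no counselor, j=1 to 3: (28+7+1)/84 = 36/84 = 0.43
- Sum 1.93 per block; 1.93/9 = 21.4%; × 30 = about 58 of 270, made up of 45 known as counselor and about 13 known as no counselor

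**Best guess.** With remaining counts s summing to n, the expected number of correct guesses is g(s) = max(s)/n + Σ (s_i/n) g(s with one fewer of i), and g = 0 for an empty block.

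- Exact arm: 53.2%, against 33.3% by chance
- Counselor or not: 72.8%, against 66.7% for always guessing counselor. The gain of 6.1 points is about 16 of 270 (0.061 × 270).

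**Blocks of 10 (4:3:3, pattern known).** 13.2% are certain as to arm. From referral alone, 17.7% are certain if the extra place is in Arm 3 (6:4), or 21.3% if it is in Arm 1 or 2 (7:3). Keeping the other printed figure would not remove the issue.

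**Varying sizes.** For an observer who knows the set of sizes but not their order (300 simulated trials of 270, each size equally likely):

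| Blocks | Certain: arm | Certain: referral | Best guess: arm | Best guess: referral |
|---|---|---|---|---|
| Fixed 9 (exact) | 14.3% | 21.4% | 53.2% | 72.8% |
| 3, 6, 9 | 4.0% | 4.1% | 55.4% | 73.8% |
| 6, 9, 12 | 2.5% | 2.2% | 52.8% | 71.8% |

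The 3/6/9 mix cuts certainty but makes guessing slightly easier, because short blocks are themselves predictable: a fixed block of 3 gives a best guess of 61.1% for arm. The 6/9/12 mix cuts certainty further and does not raise guessing accuracy.

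**The case against.** The strongest reply is that the people who know most do not recruit. The 14% and 53% figures need full knowledge of past arms. The coordinator and data manager would have it, but they act after consent and baseline collection, and no section gives them a part in screening. This stands: those figures do not describe what a recruiter knows.

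A referral-only observer gains little. The best guess improves by about 6 points, most of the certain cases are certain to be the likelier outcome, and referral does not separate Arm 1 from Arm 2. This also stands.

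A reader might infer that the trial is open-label, that everyone at the clinic can see referrals, that all staff hold the block size, or that RAs decide when a person is brought forward. The documents support none of these as stated fact. The RAs are described as blinded. Who holds the protocol and who sees referrals is not described. The clinic sees 200 adults a day (section 5.3), and people are identified by clinic staff when already due for an appointment. Deferral is a protection for unsure participants (section 5.2.3), not a timing tool for staff. Equally, nothing says how RAs are kept from noticing who goes to the counselor, and the blinding statement does not cover the staff member who makes the first approach.

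The plan has some protection downstream: adjustment for baseline drinking days, adjustment for Table 3 characteristics (including a readiness-to-change scale) that differ at p ≤ 0.1, and PEth alongside self-report. This reduces the concern without removing it. Adjustment reaches only what is measured, and PEth guards against under-reporting rather than against arms that differ in who was enrolled.

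**Conclusion.** The point holds as a modest, cheaply reduced risk. The protocol prints two conflicting constant block sizes, with no variation and no withholding, at a single clinic where referral reveals part of the allocation. With blocks of 9, at most about 21% of allocations are certain as counselor or no counselor from referral alone, and 14% are certain as to arm if all past arms are known.

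These upper bounds assume an observer who knows the block size and block starts and misses no earlier allocation. That recruiting staff can see referrals is plausible but inferred. Because consent and baseline measures come before randomization, the exposed steps are approach, eligibility and consent for coming patients. No bias in drinking days can be estimated from the documents, and the planned power is unaffected.

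It would be too strong to conclude that allocation is openly predictable to recruiters, or that varying the blocks would secure RA blinding. If RAs see referrals, they learn that those participants are in an active arm or in control, whatever the block size.

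**What to change.** Reconcile sections 5.3 and 5.5 into one description: one concealment tool, one statement of who allocates, and one blocking rule. In that rewrite:

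- Replace the fixed block with permuted blocks of randomly varying size in multiples of three, such as 6, 9 and 12 rather than 3, 6 and 9. Ten blocks of each size total 10 × (6+9+12) = 270, which keeps 90 per arm. The simulated figures are for sizes drawn independently, not for exactly ten of each.
- Have the list prepared by someone not involved in recruitment, and keep the sizes in a document that is not held at the site.
- State separately how RAs are kept from seeing who is referred to the counselor, since varying the blocks does not address this.

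The cost is a new list and a few sentences. The live-booster load is still spread; the downside is slightly less regular spacing of Arm 1 enrollments.

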5.6. Specimen collection and laboratory procedures

DBS collection and testing. DBS collection will occur at the baseline, 6-month, and 9-month study visits. Six 50 µl drops of blood will be collected onto two Whatman 903 filter papers (3 spots each), which will be allowed to dry for ≥24 hours, and then stored packaged with a desiccant in a -80C freezer at the MUST laboratory.¹²⁷

Viral suppression: Plasma HIV viral load will be measured at baseline and 9 months using the Cepheid Xpert HIV-1 RNA assay, run on an existing GeneXpert platform in Mbarara, Uganda, that has been in use for our ongoing trials.

PEth levels: The DBS card will be tested for PEth level at the United States Drug Testing Laboratories using liquid chromatography-tandem mass spectrometry (LC/MS/MS) as described.¹²⁹ We will obtain a Materials Transfer Agreement to ship the DBS to the U.S.; no laboratories in Africa conduct this test.

5.7. Measurements

5.7.1. Outcome variables

Efficacy analyses Outcome variables The primary outcome variable will be the number of days drinking (prior 3 weeks, TLFB) at 6 and 9 months. We chose this variable because (a) days drinking was the main outcome in the HWHL trial,¹⁶ (b) of several self-reported drinking variables, the number of drinking days was most highly correlated (Spearman $r=0.74$) with PEth level in a validation study in Uganda,⁹⁵ and (c) this variable may also be the least susceptible to bias because it does not require reporting the number of drinks, which can be challenging where non-standard drinks are common.⁹ We will use PEth level as an objective measure of prior 21-day alcohol use to confirm the findings obtained using self-report. Another main outcome variable will be HIV viral suppression at 9 months. Secondary outcomes will include the AUDIT-C score, which was associated with increased mortality in HIV-infected drinkers,¹³ and the number of heavy drinking days ($\geq 4/5$ drinks per occasion by females/males, respectively), the standard measure for pharmacotherapy trials. Other exploratory outcomes will include CD4 cell count and ART adherence.

Booster uptake and satisfaction Outcome variables Tech booster uptake will be measured from data extracted from the technology databases that record the SMS and IVR interactions. Uptake will be the proportion of sessions in which the participant answered all the questions prior to the final sign-off message; the denominator for this will be the number of tech booster sessions initiated by the system. Live booster call uptake will be tabulated from the counselor's call record forms that will be entered weekly into the study database. We will also determine the proportion of participants who request a counselor call back. We will also calculate intervention satisfaction in each arm using the Client Satisfaction Scale-8.¹⁴⁵ Among those in the tech booster arm (Arm 2), we will calculate usability via the System Usability Scale, used to evaluate new technology,^{146,147} and the proportions that chose SMS over IVR, overall and by reading literacy (yes/no).

Independent variables The predictor variable will be study arm by month (6 or 9 months).

